19.3 Causality and Severity Assessments

The investigator will promptly review documented adverse events and abnormal test findings to determine 1) if the abnormal test finding should be classified as an adverse event; 2) if there is a reasonable possibility that the adverse event was caused by the study drug(s) or device(s); and 3) if the adverse event meets the criteria for a serious adverse event.

If the investigator's final determination of causality is "unknown and of questionable relationship to the study drug(s) or device(s)", the adverse event will be classified as associated with the use of the study drug(s) or device(s) for reporting purposes. If the investigator's final determination of causality is "unknown but not related to the study drug(s) or device(s)", this determination and the rationale for the determination will be documented in the respective subject's case history.

19.4 Reporting of Adverse Reactions and Unanticipated Problems to the FDA

19.4.1 Written IND/IDE Safety Reports

The Sponsor-Investigator will submit a written IND Safety Report (i.e., completed FDA Form 3500A) to the responsible new drug review division of the FDA for any observed or volunteered adverse event that is determined to be a serious and unexpected, suspected adverse reaction. Each IND Safety Report will be prominently labeled, "IND Safety Report", and a copy will be provided to all participating investigators (if applicable) and sub-investigators.

Written IND Safety Reports will be submitted to the FDA as soon as possible and, in no event, later than 15 calendar days following the Sponsor-Investigator's receipt of the respective adverse event information and determination that it meets the respective criteria for reporting.

For each written IND Safety Report, the Sponsor-Investigator will identify all previously submitted IND Safety Reports that addressed a similar suspected adverse reaction experience and will provide an analysis of the significance of newly reported, suspected adverse reaction in light of the previous, similar report(s) or any other relevant information.

Relevant follow-up information to an IND Safety Report will be submitted to the applicable review division of the FDA as soon as the information is available and will be identified as such (i.e., "Follow-up IND Safety Report").

If the results of the Sponsor-Investigator's follow-up investigation show that an adverse event that was initially determined to not require a written IND Safety Report does, in fact, meet the requirements for reporting; the Sponsor-Investigator will submit a written IND Safety Report as soon as possible, but in no event later than 15 calendar days, after the determination was made.

19.4.2 Telephoned IND Safety Reports – Fatal or Life-threatening Suspected Adverse Reactions

In addition to the subsequent submission of a written IND Safety Report (i.e., completed FDA Form 3500A), the Sponsor-Investigator will notify the responsible review division of the FDA by telephone or facsimile transmission of any unexpected, fatal or life-threatening suspected adverse reaction.

The telephone or facsimile transmission of applicable IND Safety Reports will be made as soon as possible but in no event later than 7 calendar days after the Sponsor-Investigator's receipt of the respective adverse event information and determination that it meets the respective criteria for reporting.

19.5 Reporting Adverse Reactions and Unanticipated Problems to the Responsible IRB

In accordance with applicable policies of The Pennsylvania State University Institutional Review Board (IRB), the investigator will report, to the IRB, any observed or reported harm (adverse event) experienced by a subject or other individual, which in the opinion of the investigator is determined to be (1) unexpected; and (2) probably related to the research procedures. Harms (adverse events) will be submitted to the IRB in accordance with the IRB policies and procedures.

19.6 Unblinding Procedures

The Investigational Pharmacy at Penn State Hershey Medical Center and they will hold the randomization and unblinding key as needed. The investigators and biostatisticians will remain blinded to the allocation sequence and patient assignment. Investigator will have the discretion of unblinding the physicians at any time if it is warranted for safety and/or scientific reasons.

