3.0 Inclusion and Exclusion Criteria

3.1 Inclusion Criteria

Inclusion

- Premenopausal female ages 18 to 45 years old on the day of signing informed consent.
- Must agree to use only study-specific analgesic medications during the study and is not known to be intolerant to them.
- Diagnosed with endometriosis and has had, within the last 10 years prior to signing the informed consent, surgical diagnosis with direct visualization and/or histopathologic confirmation of endometriosis.
- Is not expected to undergo gynecological surgery or other surgical procedures for treatment of endometriosis during the study period.
- Agrees to use contraception if not surgically sterile during the entire study.
- Patients using oral contraceptives, LARCs and/or GnRH agonists/antagonists for contraception and/or management of endometriosis, with a stable regimen, will be able to continue in the study, however, women using oral contraceptives and GnRH agonist/antagonists will be switched to Norethindrone acetate during the 1-2 week run-in period as prescribed by principle investigator.

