3.3.2 Follow-up for withdrawn subjects

The statistical methods allow for withdraw/screen fails. Subjects will be asked to return the study drug to the site if withdrawn or removed from the study. No other safety follow-up planned.

If the subject is removed from the study for any of the above reasons, she will receive the appropriate treatment based on the decisions of her providing physician team. No further data will be collected on these patients.

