The study will include a 12-week intervention period during which subjects will be asked to record daily electronic VAS scores, report daily analgesic use (NSAIDs and opioids) and complete surveys every 4 weeks. VAS scores will be reported daily. Patient Global Impression of Change (PGIC), Patient Global Assessments (for pain, dysmenorrhea, nonmenstrual pelvic pain and function) (PGAs) and Endometriosis Health Profile-30 (EHP 30) surveys will be completed at 4-week intervals during the intervention (0, 4, 8, and 12 weeks). Subjects will be asked to complete a brief telephone interview visit at 16 weeks to complete final quality of life surveys (EHP 30, PGAs and PGIC).

Subjects will be screened for side effects and asked to record pain medication use throughout the duration of the study. Subjects will be dispensed a 4-week supply of medications from the Investigational Pharmacy. They will be required to bring medication bottles to each visit for counting and drug accountability. Any remaining capsules will be returned to the pharmacy. All study subjects and investigators will remain blinded to the study group until the completion of the study. In the event subjects cannot attend study visits in-person due to extenuating circumstances (e.g. related to COVID-19 pandemic), remote visits can be completed via telephone for which questionnaires will be sent via REDcap and IDS will ship of study drug. Drug accountability and monitoring for side effects can also be done via telephone.

Procedure	Pre- screen	Screening Visit (beginning of Run-in week)	Visit 1 Enrollment – Randomization (Day 1)	Visit 2* 4-weeks (Day 28- 30)	Visit 3* 8-weeks (Day 56- 58)	Visit 4* 12-weeks (Day 84- 86)	Visit 5 16-weeks Phone f/u (Day 114- 121
Screening Criteria	Х						
Informed Consent		X					
WERF Questionnaire		Х					
Physical		Х					
Past Medical History		Х					
EHP-30		Х	Х	Х	Х	Х	Х
PGIC				X	X	X	Х
PGAs		Х	Х	Х	X	Х	Х
Study Drug Dispensed & Compliance		X (Only Norethindrone Acetate given, if needed)	Х	Х	Х	Х	
Daily Pain, Analgesic and Study Medication Assessment		X (6-7 days)	X (Daily)	X (Daily)	X (Daily)	X (Daily)	X (Daily)
Screening/Assessment of Adverse Events		X	Х	X	X	X	Х

Visit Table Summary of Study Procedures

(*) - these asterisked visits can be done remotely via telephone, if warranted due to extenuating circumstances.

7.2.1 Screening visit:

Screening Visit 1:

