Study subjects will receive education on analgesics approved for use in the study which are also within the standard of care for the management of pelvic pain associated with endometriosis. As standard of care for these patients, study subjects will be instructed to take ibuprofen as first time treatment and acetaminophen if additional pain relief is needed, both of which are available over the counter. Only if requested will a stronger medication be prescribed like oxycodone. If needed, to relieve pain, the subject will be advised to take first the ibuprofen 600 mg every 6 hours as needed for pain with food, then acetaminophen 1000mg every 6 hours as needed for pain. Subjects needing additional pain relief will need to discuss this with the study team in which oxycodone 5 mg every 6 hours as needed for pain will be prescribed. Refill prescriptions for opioid pain medication will be provided using the same dose and quantity beyond the screening visit on an as needed basis and will not be routinely provided at any subsequent study visits unless there is a documented need. The subject will complete an EPH-30 and PGAs surveys at the visit. The subject will be instructed to complete their daily surveys which include the VAS and medication compliance. We will also review and record any adverse events. At this time, we will also review compliance of daily reporting since the previous visit. Surveys will be sent via email through a secure link with RedCap and completed on-site during the visit.

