7.4.5 Blinding of the Test Article

The naltrexone, norethindrone acetate, and placebo will be provided in individual packets that will be identical. The drug will be kept and dispensed in the Investigational Pharmacy at Penn State Hershey Medical Center and they will hold the randomization and unblinding key as needed. The investigators and biostatisticians will remain blinded to the allocation sequence and patient assignment.

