7.4.6 Receiving, Storage, Dispensing and Return

7.4.6.1 Receipt of Test Article

The naltrexone, norethindrone acetate, and placebo will be monitored and dispensed by our Investigational Drug Services (IDS) Pharmacy. IDS will hold the randomization and unblinding key as needed. Participants will be given study drug to take one daily as prescribed.

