16.3 PI Time devoted to conducting the research

The PI has dedicated research time and is available to see study patients 2-3 days/week and the co-Investigator on the study asback up.

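### Section 19.6 permits unblinding of physicians at any time on an undefined scientific ground for which the plan states no use

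*Combined protocol and SAP*

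**What the plan says.** The unblinding rule is the last sentence of Section 19.6: "Investigator will have the discretion of unblinding the physicians at any time if it is warranted for safety and/or scientific reasons". It names the decision-maker (the investigator), the people who may be told (the physicians), the timing (any time) and two grounds (safety, science). The physicians are not identified and the scientific ground is not defined.

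Three other statements promise blinding:

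- Section 7.1: "All study subjects and investigators will remain blinded to the study group until the completion of the study".
- Section 7.4.5: "The investigators and biostatisticians will remain blinded to the allocation sequence and patient assignment".
- Section 19.6 itself repeats the 7.4.5 sentence directly before the unblinding rule.

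None of the three states an exception. The code is held by the pharmacy; Section 7.4.6.1 says "IDS will hold the randomization and unblinding key as needed", without saying what counts as a need.

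**The concern.** A code break for safety is a normal part of a blinded drug trial, and nothing here questions it. The second ground is different. As worded, it lets the investigator reveal assignments before the trial ends for a reason that no section describes and that nobody else is said to approve.

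Two things are at stake. The first is the blind itself: a non-safety disclosure made before completion is avoidable and cannot be undone. The second arises only if study physicians are among those told. Study staff have some discretion over oxycodone, and opioid intake is both a covariate in the primary model (Section 8.3) and a secondary outcome (Section 1.3). The investigator also judges whether an adverse event was caused by the study drug (Section 19.3). Knowing the arm could colour either decision.

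**Working it through.** No arithmetic applies. The documents give no expected number of code breaks and nothing from which their effect could be computed. The check is a comparison of the text in four steps.

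**1. Does the plan give the scientific ground a use?** These are the places where one might be expected:

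| Section | What it provides | Use for an early code break? |
|---|---|---|
| 7.4.3 Assignment | Independent statistician prepares the seeds; pharmacy randomizes, so that the study team and its statisticians stay blinded | None |
| 8.3 Statistical methods | Analyses of the trial data; no interim efficacy analysis | None |
| 10.7 Statistical tests | Refers to 10.2, which describes no test | None |
| 10.8 Suspension of research | Marked not applicable | None |
| 19.7 Stopping rules | Six-monthly adverse event report to the principal investigator, by arm but blinded | None |

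No section supplies a purpose. Sections 7.4.3 and 19.7 take care to avoid revealing assignments.

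**2. Who are the physicians?** There are two readings.

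- *Outside providers.* Section 3.3.2 says that a subject removed from the study is then treated by her own doctors: "she will receive the appropriate treatment based on the decisions of her providing physician team". Section 19.6 also words the physicians separately from the investigators in the sentence before.
- *Study physicians.* The clinical roles overlap with the investigator role. Section 3.1 has some subjects "switched to Norethindrone acetate during the 1-2 week run-in period as prescribed by principle investigator", and Section 16.3 says "The PI has dedicated research time and is available to see study patients 2-3 days/week", with a co-investigator as back-up.

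The text does not settle which is meant.

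**3. What follows from each reading?**

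- If only outside providers are meant, the three blinding statements and the rule can stand together. The scientific ground still has no stated use.
- If study physicians are included, the rule contradicts Section 7.1, Section 7.4.5 and the second sentence of 19.6. Section 7.1 is the only one with an end date, but the other two are equally unqualified. Amending 7.1 alone would leave two contradictions.

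**4. How could knowledge of the arm reach the results?**

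- *Primary VAS:* subjects enter it daily through an emailed link (Section 7.1), and the rule does not name subjects among those who may be told. Any effect is indirect.
- *Oxycodone:* Section 7.2.2 says "Subjects needing additional pain relief will need to discuss this with the study team". It is given on request, refills keep dose and quantity unchanged, and refills need a documented reason. Some discretion remains, and it feeds the covariate and the secondary outcome.
- *Norethindrone adjustment:* tied to bleeding and recorded in a progress note (Section 7.1), so the room for influence is limited.
- *Adverse event causality:* a judgement by the investigator (Section 19.3), which knowledge of the arm could affect directly.

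A code break is not among the removal criteria in Section 3.3.1. A subject whose assignment was revealed for a scientific reason could therefore remain in the trial and in the analysis.

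**The case against.** The strongest reply is that there is no contradiction. Section 19.6 says in one sentence that investigators stay blinded and in the next that the investigator may unblind the physicians, which reads as two groups. Trial staff are elsewhere called investigators, PI or study team, and Section 3.3.2 speaks of physicians when it means the subject's own providers. This has force. A reader might infer that the protocol plainly authorizes unblinding of its own study team; the documents do not establish that, and the conflict is only conditional. The reply does not touch the scientific ground, which lacks a stated purpose on either reading.

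A second reply is that the primary outcome is safe: subjects are blinded and report their own pain, and oxycodone and norethindrone decisions are constrained. This largely stands. A reader might infer that the primary comparison would be biased; nothing in the documents shows that, or suggests more than isolated code breaks.

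A third is that the pharmacy may already log code breaks under procedures not reproduced here. That is possible, so it cannot be said that no record would exist. The protocol itself simply does not mention one in the study data.

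Finally, the scientific ground could be defined instead of deleted. That would also work if the sponsor has a purpose in mind. Since none is stated, deletion is the simpler course.

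**Conclusion.** The point holds in a limited form. The permission to unblind for scientific reasons is an express rule, has no stated use, and allows avoidable loss of blinding before completion. That conclusion does not depend on who the physicians are. The conflict with Sections 7.1, 7.4.5 and the preceding sentence of 19.6 does: it arises only if study physicians are included, which the text leaves open.

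The size is unknown and cannot be estimated from the documents. Any effect on the VAS would be indirect; the more direct routes are the remaining discretion over oxycodone and the judgement of causality. This is an inexpensive improvement to the protection of the blind, not evidence that the primary result would be invalid.

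**What to change.** Main change:

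- In Section 19.6, delete the words *and/or scientific reasons*. Leave the safety ground as it is.
- In Section 7.1, Section 7.4.5 and the second sentence of Section 19.6, add the same single exception, for example: *except for a code break made for safety under Section 19.6*.

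Secondary clarifications:

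- Say in Section 19.6 which physicians may be told.
- Have each code break noted in the study data (subject ID, date, reason, who was told), so that affected subjects can be identified if a sensitivity analysis is wanted. The plan does not now include such an analysis.

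The cost is a few words in three places and a short log. The investigator gives up discretionary non-safety unblinding before completion. Unblinding for safety is not reduced.

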19.7 Stopping Rules

The principle investigator will receive immediate notification of all serious adverse events, and a regular report, at six month intervals, summarizing recruitment and all adverse events, by treatment in a blinded fashion. The principle investigator will meet with research team after the receipt of the scheduled reports or after any major serious adverse event.

20.0 Study Monitoring, Auditing and Inspecting

20.1 Study Monitoring Plan

20.1.1 Quality Assurance and Quality Control

The study will be monitored by the Clinical Trial Monitoring Team from the Department of Public Health Sciences at Penn State Hershey College of Medicine. The monitors will provide an independent review of the regulatory and subject records and the data collected to assure compliance with the protocol, GCP, and applicable federal regulations. The monitoring will occur

at regular intervals after the enrollment of the first subject and the times will be predetermined by the monitoring plan developed by the Clinical Trial Monitoring Team.

20.1.2 Safety Monitoring

See Section 10.0 for data and safety monitoring plan.

21.0 Future Undetermined Research: Data and Specimen Banking

21.1 Data and/or specimens being stored

Not applicable

21.2 Location of storage

Not applicable

21.3 Duration of storage

Not applicable

21.4 Access to data and/or specimens

Not applicable

21.5 Procedures to release data or specimens

Not applicable

21.6 Process for returning results

Not applicable

